2.1 Objectives

Primary Objective — To evaluate the efficacy of memantine in treating frequent symptomatic PACs.

Secondary Objective — To assess the safety profile of memantine in patients with frequent symptomatic PACs.

2.2 Endpoints

2.2.1 Efficacy Endpoints

Primary Efficacy Endpoint: The percentage change from baseline in the 24-hour mean number of PACs at Week 6.

Secondary Efficacy Endpoints:

- a) The change from baseline in the 24-hour mean number and burden of PACs at Weeks 4, 6, and 8;
- b) The change from baseline in the 24-hour mean episode count and burden of NSAT at Weeks 4, 6, and 8;
- c) The change from baseline in the 24-hour mean episode count of SAT, AF, and AFL at Weeks 4, 6, and 8;
- d) The proportion of participants with new-onset SAT, AF, or AFL lasting ≥ 30 seconds during a continuous 72-hour monitoring period at Weeks 4, 6, and 8. This endpoint will be calculated based on the first occurrence of SAT, AF, or AFL during the respective 72-hour monitoring windows;
- e) The cumulative incidence of new-onset AF from baseline to Week 8: The proportion of participants who experience their first episode of AF lasting ≥ 30 seconds during any of the 4th, 6th, or 8th-week follow-up windows, with each participant counted only once, even if they have multiple occurrences across different follow-up windows;
- f) The change from baseline in the SF-36 quality of life score at Week 6;
- g) Efficacy analysis of PACs or NSAT, based on the proportion of responders.

2.2.2 Safety Endpoints

The incidence of AEs (including psychiatric symptoms, seizures, bradycardia and new-onset heart failure, etc.), SAEs, laboratory test abnormalities, and abnormal ECG findings.

3. Study Design

3.1 Overall Design

This investigator-initiated, multicenter, randomized, double-blind, parallel-group, placebo-controlled trial will enroll 256 adults (18–80 years of age) with frequent symptomatic PACs.

After an initial eligibility screen, all candidates will undergo 72-hour continuous patch-based ambulatory electrocardiographic monitoring to quantify baseline PAC burden. Participants who meet the inclusion criteria will be randomly assigned on Day 0, in a 1:1 ratio, to receive oral memantine or matched placebo. Randomization will be stratified according to age (≥ 65 vs. < 65 years) and baseline PAC burden (≥ 5000 vs. < 5000 PACs per 24 hours), yielding 128 participants per group (total, 256).

The protocol specifies five visits:

- Visit 1 (Screening; ≤ 14 days before randomization) — Baseline clinical assessments and 72-hour ambulatory ECG monitoring.
- Visit 2 (Day 7 ± 2 days) — Telephone contact to assess treatment compliance and solicit adverse events.
- Visit 3 (Day 28 ± 3 days), Visit 4 (Day 42 ± 3 days; end of treatment), and Visit 5 (Day 56 ± 3 days; end of study) — On-site evaluations, each including repeat 72-hour ambulatory ECG monitoring.

A schematic of the study procedures is provided in Figure 1.

[figure not shown]

Figure 1 Study Design Flowchart

The treatment phase will last 42 to 45 days. Seventy-two-hour ambulatory ECG will be initiated on study days 25 – 28 for Visit 3 (V3), days 39 – 42 for Visit 4 (V4), and

days 53 – 56 for Visit 5 (V5). For V4, monitoring must begin 72 hours before the final scheduled dose; thus, if dosing concludes on day 42, monitoring must start on day 39. Conversely, if monitoring is initiated on day 42, study medication must continue through day 45. All other assessments scheduled for V3 – V5 must be completed between placement and removal of the 72-hour ECG device.

3.2 Study Centers

The trial will be conducted at approximately 20 hospitals across China; the number of participating sites may be adjusted on the basis of operational considerations.

3.3 Randomization and Blinding

3.3.1 Randomization and Blinding

Eligible participants will be randomly assigned, in a 1:1 ratio, to receive either memantine or matching placebo. A stratified block design will be used, with randomization stratified by baseline 24-hour PAC burden (≥ 5000 vs. < 5000 PACs per 24 hours) and age (≥ 65 vs. < 65 years). An independent statistical team which is otherwise unaffiliated with the study will generate the randomization list and corresponding treatment-allocation list with SAS software (version 9.4 or higher). Both lists will be uploaded to an interactive response technology (IRT) system, which will assign each participant a unique randomization number and the corresponding study-drug kit on Day 0. Randomization and kit numbers, once issued, will not be reused. Participants who withdraw from the study—irrespective of drug exposure—will not be re-enrolled.

3.3.2 Blinding

This is a double-blind trial: investigators, participants, and site personnel—including monitors, data managers, and statisticians—will remain unaware of treatment allocation until the prespecified unblinding conditions are met. Placebo tablets are identical to active tablets in appearance, odor, weight, packaging, and dosing schedule but contain no active memantine. Blinding will be maintained from generation of the randomization code through drug dispensing, data collection, monitoring, data management, and statistical analysis.

3.3.3 Emergency Unblinding

Unblinding is permitted only when a participant experiences a medical emergency in which knowledge of the assigned treatment is indispensable for appropriate management. If emergency unblinding is not required to manage the event, the blind must be maintained.

- The investigator must document the date, time, reason, and personnel involved in the unblinding and notify the study monitor without delay.
- A safety report must be submitted to the institutional ethics committee as soon as possible.
- The participant must discontinue study medication but will remain in the study for continued follow-up; the reason for treatment discontinuation must be recorded in the case-report form.
- At study close-out, the frequency, reasons, extent, and timing of all emergency unblinding will be summarized and evaluated for their potential impact on efficacy and safety analyses.

In the event of an unexpected SAE, individual unblinding will be performed according to the same procedure to determine whether the SAE constitutes a suspected unexpected serious adverse reaction (SUSAR). All other study personnel will remain blinded, and the participant will not be considered lost to follow-up.

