8.2.3 Causality

The investigator is responsible for assessing the causality between each AE recorded in the eCRF and the investigational product. This evaluation will be based on all available information at the time of completing the eCRF and is a clinical judgement.

The causality will be classified into one of five categories based on the plausibility of a relationship between the AE and the investigational product: *related*, *very likely related*, *possibly related*, *possibly unrelated*, and *unrelated*. Events classified as *related*, *very likely related*, or *possibly related* will be considered to have a potential or cannot be excluded as related to the study treatment, and will be classified as *related*. Events categorized as *possibly unrelated* or *unrelated* will be classified as *unrelated*.

When assessing the causal relationship between an AE and the study treatment, the following factors should be considered:

Related: There is a reasonable temporal relationship; the event aligns with the known pharmacological mechanism, characteristics, or known adverse effects of the investigational product; the event is positively dechallenged; no other reasonable explanation exists for the event; and the event is positively rechallenged.

Very Likely Related: There is a reasonable temporal relationship; the event aligns with the known pharmacological mechanism, characteristics, or known adverse effects of the investigational product; the event is positively dechallenged; no other reasonable explanation exists for the event; and there is no evidence of positive rechallenge.

Possibly Related: There is a reasonable temporal relationship; there is no evidence of positive rechallenge; and the event falls into one of the following categories:

- (1) The event is consistent with the known pharmacological mechanism, characteristics, or known adverse effects of the investigational product; the event is positively dechallenged, but other plausible explanations exist.
- (2) The event is consistent with the known pharmacological mechanism, characteristics, or known adverse effects of the investigational product; there is no evidence of positive dechallenge, and no other plausible explanations exist.
- (3) The event is not consistent with the known pharmacological mechanism, characteristics, or known adverse effects of the investigational product; the event is positively dechallenged, and no other plausible explanations exist.

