In cases of death, the cause of death should be recorded as the AE term. The term “death” should not be used as the AE term itself. The cause of death should be documented as the AE outcome. If the cause of death is initially unknown, it should be reported as “cause of death unknown” and monitored until the cause is determined. Once the cause of death is clarified, the SAE term should be updated to reflect the specific cause of death.

The investigator must independently assess all SAEs, evaluating their expectedness, severity, and the causal relationship with the investigational product.

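### Protocol 3.3.3 reserves unblinding for emergencies but then unblinds any unexpected SAE, without a relatedness condition, a prior blinded causality rating or a named recipient of the code

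*Protocol*

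**What the plan says.** Protocol 3.3.3 (Emergency Unblinding) opens with a restriction: "Unblinding is permitted only when a participant experiences a medical emergency in which knowledge of the assigned treatment is indispensable for appropriate management". It adds: "If emergency unblinding is not required to manage the event, the blind must be maintained". A list of steps follows, and the only role named in it is the investigator: "The investigator must document the date, time, reason, and personnel involved in the unblinding and notify the study monitor without delay".

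The last paragraph of the section covers a different case: "In the event of an unexpected SAE, individual unblinding will be performed according to the same procedure to determine whether the SAE constitutes". The question to be settled there is SUSAR status. It continues: "All other study personnel will remain blinded". The people who do not remain blinded are not identified.

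Causality is dealt with elsewhere. Protocol 8.2.3 says: "The investigator is responsible for assessing the causality between each AE recorded in the eCRF and the investigational product", and bases the rating on whatever information is at hand when the eCRF is filled in. Protocol 8.3 says: "The investigator must independently assess all SAEs, evaluating their expectedness, severity, and the causal relationship with the investigational product". Neither section says whether the rating comes before or after a code break.

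SAP 4.3.2.1 and 4.3.2.2 tabulate treatment-related SAEs and treatment-related TEAEs, including those leading to death, discontinuation and withdrawal, next to the all-cause rows.

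**The concern.** A site with an unexpected SAE that can be managed without the code has two opposite instructions in one section. If it follows the last paragraph, the blind is broken for a classification purpose, and also for events that nobody links to the study drug.

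The blinded causality rating is also at stake. A rater who knows that the participant took placebo will tend to call an event unrelated, and one who knows that the participant took memantine will tend to call it related. If that can happen, the treatment-related rows of the safety tables no longer carry only blinded clinical judgement. Safety is the trial's secondary objective, so those rows will be read.

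**Working it through.** No figure in the plan bears on this point, so the check is a comparison of the text.

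**1. What the two parts of 3.3.3 require, case by case**

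- Unexpected SAE, code needed for care: both parts lead to unblinding. No conflict.
- Unexpected SAE, code not needed, suspected to be drug-related: the opening keeps the blind and the last paragraph breaks it. The parts conflict, although the SUSAR purpose is genuine.
- Unexpected SAE, code not needed, not suspected to be drug-related: the same conflict. The event is not a suspected reaction, so it cannot be a SUSAR, and the code break achieves nothing.
- Expected SAE, code not needed: both parts keep the blind. No conflict.

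The conflict covers the two middle cases. The third case shows that the trigger is too wide.

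**2. What is left to determine**

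By the protocol's own term, a SUSAR is serious, unexpected and a suspected reaction. When the last paragraph applies, seriousness and unexpectedness are already given, so only suspected relatedness is open. Sections 8.2.3 and 8.3 give that judgement to the investigator. Allocation cannot replace it: knowing that a participant took memantine does not make an event suspected.

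**3. Whether causality must be rated blind**

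- 3.3.3: sets no order between the rating and the code break.
- 8.2.3: uses all information at hand, so a known allocation is not excluded.
- 8.3: requires an independent assessment but gives no time point relative to unblinding.
- SAP: has no rule on which rating to use if the code was opened, and no listing of code breaks.

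**4. Who learns the allocation**

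The text borrows the emergency procedure, in which the investigator documents the event and the people involved. It does not say who opens the code, who receives it or who decides SUSAR status. The documents mention an IRT system and an independent team that generates the lists (3.3.1) and a randomization manager who releases codes at the end (3.3.4). None of them is given a role for a single case.

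**5. Size**

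Neither document gives an SAE rate, so the number of code breaks cannot be computed. For scale only, under an assumed 2% to 5% of participants with an unexpected SAE: 0.02 × 256 = 5.1 and 0.05 × 256 = 12.8, or about 5 to 13 participants. How many of these would be rated related is unknown.

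**The case against.** The strongest defence is that the text is silent rather than wrong. The trigger presupposes that expectedness has been judged. Section 8.3 makes expectedness, severity and causality one investigator duty, and 8.4 requires the SAE report within 24 hours. A site could rate causality first and have the code opened afterwards. The last paragraph can also be read as a second, specific condition, since 3.3.2 speaks of prespecified unblinding conditions in the plural.

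Much of this stands. A reader might infer that the code is always opened before causality is judged, or that the site investigator does receive it. The documents say neither; both are likely readings of a gap. The plural in 3.3.2 does not remove the conflict, because 3.3.3 sets the conditions and itself uses the word only.

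Other safeguards exist. The eCRF audit trail (10.1) would show a rating that was changed after a code break, but not one first entered after it. Section 3.3.3 promises a close-out evaluation of emergency unblinding; whether that includes SUSAR code breaks is unclear, and the SAP does not implement it. The safety tables are descriptive, and all-cause counts do not depend on relatedness. Stopping study drug is not an added consequence of the code break, because 5.2 and 8.2.4 already prescribe it after any SAE following randomization.

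Finally, the SAP revision history puts enrollment near 256 before version 2.0, so a protocol edit may affect few participants. That stands too.

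**Conclusion.** The point holds in a limited form. Section 3.3.3 contradicts itself. Its SAE trigger has no relatedness condition, which goes beyond a missing detail: followed as written, it breaks the blind for events that cannot be SUSARs. The plan does not protect the blinded causality rating, so the investigator who makes it may know the allocation.

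The possible harm is confined to the treatment-related rows of descriptive safety tables. No hypothesis test uses relatedness, and the effect on the ECG-derived primary endpoint is small. A reader might infer that all or most of the treatment-related SAE table would be compromised. The documents do not support that, since they give no SAE rate, no order of steps and no recipient of the code. The concern about bias assumes that allocation reaches the causality rater before the rating is recorded; the contradiction and the over-wide trigger need no such assumption.

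It is worth correcting because the correction is cheap. It does not threaten the primary result.

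**What to change.** **Protocol 3.3.3**

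- Make SUSAR unblinding a separate, stated exception to the emergency-only rule, with its own procedure.
- Require the investigator to record causality and expectedness while blinded.
- Unblind for SUSAR reporting only SAEs rated both unexpected and related, using the related grouping in 8.2.3.
- Have the existing holder of the randomization codes release the code to a named recipient outside the site and the analysis team. The investigator, site staff, monitor and trial statistician stay blinded unless the emergency rule applies.

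**SAP**

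- List all code breaks, emergency and SUSAR, and flag whether causality had been recorded beforehand.
- Base the treatment-related tables on the causality recorded before any code break. State how events without such a rating are handled, because SAP 3.2.2 would code a missing rating as treatment-related.

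**Cost**

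One protocol paragraph, one or two SAP sentences and one extra step in SUSAR handling. The code holder exists, but a case-level duty and a recipient must be assigned, since the documents name no safety function. With enrollment nearly complete, the protocol edit may reach few participants; the SAP change is still useful if made before unblinding.

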3.3.4 Final Unblinding

After the database lock, confirmation of analysis populations, and finalization of the statistical analysis plan, the study statistician will submit a written request for final unblinding. The request must be countersigned by the principal investigator and the statistician. Upon receipt of the signed approval, the randomization manager will release the treatment codes.

4. Study Population

4.1 Inclusion Criteria

(1) Age: 18 to 80 years, inclusive.

(2) Symptomatic PACs: Documented at screening as $\geq 1,000$ PACs during a 24-hour ambulatory ECG recording.

(3) Informed consent: Ability and willingness to understand and comply with all study procedures and to sign the written informed-consent form before any protocol-specific activities are performed.

4.2 Exclusion Criteria

(1) Atrial or ventricular arrhythmias

AF, AFL, or SAT documented by 12-lead ECG within 6 months before screening or detected on the baseline 72-hour patch-type ambulatory ECG;

Ventricular tachycardia (excluding brief nocturnal runs) or ventricular fibrillation.

(2) Recent cerebrovascular or cardiac events

Ischemic or hemorrhagic stroke, or transient ischemic attack, within 6 months before screening;

Cardiac surgery, myocardial infarction, percutaneous coronary intervention, or catheter ablation for atrial arrhythmias within 3 months before screening.

(3) Severe cardiac dysfunction

Left-ventricular ejection fraction $\leq 40\%$;

New York Heart Association class III or IV heart failure.

(4) Clinically significant conduction disease

Sick-sinus syndrome without a permanent pacemaker.

Second-degree type II or higher atrioventricular block, or bifascicular block.

(5) Recent antiarrhythmic therapy

Amiodarone within 4 weeks before screening;

Any other antiarrhythmic agent—including herbal preparations with antiarrhythmic properties—within 1 week before screening.

f) Other serious cardiac conditions

Unstable angina, severe congenital heart disease (except patent foramen ovale), prior prosthetic heart-valve replacement, acute myocarditis or endocarditis, rheumatic valvular disease, or hypertrophic obstructive cardiomyopathy.

g) Limited life expectancy

Any comorbid condition with an anticipated survival of < 1 year.

h) Hepatic impairment

Active hepatitis or clinically significant liver dysfunction (ALT or AST $> 3 \times$ ULN, or total bilirubin $> 3 \times$ ULN).

i) Renal impairment

Estimated glomerular filtration rate $< 40 \text{ mL} \cdot \text{min}^{-1} \cdot 1.73 \text{ m}^{-2}$ (CKD-EPI formula).

(10) Concurrent investigational therapy

Use of any investigational drug or device within 1 month—or five elimination half-lives, whichever is longer—before screening.

(11) Pregnancy or lactation

Pregnant or breastfeeding women, or a positive serum pregnancy test before randomization.

(12) Metabolic, surgical, or pulmonary instability

Uncontrolled hyperthyroidism.

Perioperative cardiothoracic surgery — defined as the interval from 1 week before to 2 weeks after the procedure;

Uncorrected electrolyte imbalance (serum potassium $> 5.5 \text{ mmol/L}$ or $< 3.5 \text{ mmol/L}$; serum magnesium $< 1.5 \text{ mmol/L}$);

Chronic obstructive pulmonary disease with respiratory failure or active, uncontrolled infection.

(13) Neurologic or psychiatric disorders

History of epilepsy, seizures, or psychiatric illness that could interfere with study participation.

(14) Drug hypersensitivity

Known allergy to memantine hydrochloride or any excipient of the study drug.

(15) Current memantine therapy

Ongoing treatment with memantine for moderate-to-severe Alzheimer's disease.

(16) Other contraindications

Any condition that, in the investigator's judgment, makes the participant unsuitable for enrollment in the study.

4.3 Withdrawal Criteria

4.3.1 Participant-Initiated Withdrawal

4.3.1.1 Discontinuation of Study Drug

Investigators should make every reasonable effort to keep participants on their assigned study drug. If, after full counselling, a participant unequivocally requests discontinuation, dosing must cease. The participant should complete the early-termination visit and remain in the trial for all subsequent protocol-specified assessments.

4.3.1.2 Withdrawal from the Trial

A participant is considered withdrawn from the trial if either of the following occurs:

- **Lost-to-follow-up:** the participant fails to complete the final protocol-specified visit.
- **Death.**

4.3.2 Investigator-Initiated Withdrawal

4.3.2.1 Discontinuation of Study Drug

The investigator may discontinue study treatment for safety or other compelling reasons, including:

- (1) Medical or ethical considerations that, in the investigator's judgement, necessitate cessation of treatment.
- (2) Allergic reactions, neuropsychiatric symptoms, or any other SAE requiring discontinuation.
- (3) An emergent clinical condition mandating alternative therapy.
- (4) Any unforeseen circumstance that, in the investigator's judgement, warrants early termination of treatment.

Participants who discontinue study drug for any of the above reasons must complete the early-termination visit and continue follow-up as outlined in the protocol (on-site or by telephone).

4.3.2.2 Withdrawal from the Trial

Although every effort should be made to ensure that participants complete all scheduled visits, the investigator may withdraw a participant if circumstances arise that preclude

further participation. All protocol-specified early-termination assessments must be completed before withdrawal.

4.4 Procedures for Early Withdrawal

Participants who discontinue early—either by stopping study medication or by formally withdrawing from the trial—must complete an early-termination visit. At that visit, the investigator shall document the withdrawal date, reason, and all pertinent clinical information.

(1) Participant-initiated withdrawal

The investigator must determine and record the participant's reason for withdrawal and establish whether any AEs are involved.

All AEs must be entered into the electronic case-report form (eCRF) and followed to resolution or clinical stabilization.

(2) Data collection

Every effort should be made to capture all available data from participants who discontinue, with special attention to potential endpoint events. Complete loss to follow-up threatens data integrity and should be avoided whenever possible.

(3) Follow-up

Participants who stop study drug should continue protocol-specified assessments at the scheduled time points.

If a participant declines in-person visits but agrees to telephone follow-up, remote assessments will be conducted until study completion.

Participants who refuse all forms of follow-up will be considered lost to follow-up; this status must be recorded in the eCRF.

(4) Study-drug accountability

All unused investigational product must be retrieved at the early-termination visit and reconciled in the drug-accountability log.

5. Investigational Products

